11.1.5 Serious Adverse Events or Serious Suspected Adverse Reactions

As defined in the Code of Federal Regulations (21 CFR 312.32), an adverse event or suspected adverse drug reaction is considered "serious" if, in the view of either the investigator or the sponsor, it results in any of the following outcomes:

- Death;
- A life-threatening adverse event (Note: An adverse event or suspected adverse reaction is

considered “life-threatening” if, in the view of either the investigator or sponsor, its occurrence places the subject in immediate risk of death. It does not include an adverse event or suspected adverse event that, had it occurred in more severe form, might have caused death. The determination of whether an adverse event is life-threatening can be based on the opinion of either the investigator or sponsor.);

- Inpatient hospitalization or prolongation of existing hospitalization;
- A persistent or significant incapacity or substantial disruption of the ability to conduct normal life functions; or
- A congenital anomaly/birth defect.

Important medical events that may not result in death, be life-threatening, or require hospitalization may be considered serious when, based upon appropriate medical judgment, they may jeopardize the subject and may require medical or surgical intervention to prevent one of the outcomes listed in the definition.

If either the sponsor or investigator believes that the event is serious, the event must be considered serious and evaluated by the sponsor for expedited reporting.

11.1.6 Definition of Hospitalization

Adverse events reported from clinical trials that result in hospitalization or prolong an existing hospitalization are considered serious. Any initial admission (even if less than 24 hours) to a healthcare facility meets these criteria.

Outpatient ambulatory surgical procedures (same-day surgeries) and routine emergency room treatment do not qualify as hospitalizations. Additionally, hospitalization in the absence of a precipitating clinical adverse event is not in itself an SAE. Examples include, but are not limited to any of the following:

- Admission for treatment of a pre-existing condition not associated with the development of a new adverse event or with a worsening of the pre-existing condition (e.g., for work up of persistent pre-treatment abnormality);
- Administrative admission (e.g., for yearly physical examination);
- Optional admission not associated with a precipitating clinical adverse event (e.g., for elective cosmetic surgery); or
- Pre-planned treatments or surgical procedures should be noted in the baseline documentation for the entire protocol and/or for the individual subject.

Diagnostic and therapeutic non-invasive and invasive procedures, such as surgery, should not be reported as adverse events. However, the medical condition for which the procedure was performed should be reported if it meets the definition of an adverse event. For example, an acute appendicitis that begins during the adverse event reporting period should be reported as the adverse event, and the resulting appendectomy should be recorded as treatment of the adverse event.

11.2 Eliciting Adverse Event Information

The investigator is to report all directly observed adverse events and all adverse events spontaneously reported by the study subject. In addition, study subjects should be questioned by site personnel about adverse events at each clinic visit using a standard non-leading question, such as “Have you experienced anything new or different since your previous study visit?”

Certain adverse events require prompt and specific action by the investigator in any clinical trial.

11.3 Reporting Period

The reporting period for adverse events begins when the subject provides written informed consent and extends until 28 calendar days after the last day of study participation. All adverse events that occur during this period and are known to the investigator must be reported according to the requirements outlined in this protocol.

11.4 Reporting Requirements

All adverse events will be reported on the adverse event page of the CRF. In addition, serious adverse events must also be reported on a separate SAE Form. For cases in which the same data are collected, the forms must be completed in a consistent manner. For example, the same adverse event term should be used on both forms. Adverse events should be reported using concise medical terminology on the CRFs as well as on the form for collection of serious adverse events or suspected adverse reactions information.

11.4.1 Serious Adverse Event Reporting Requirements

If an SAE occurs, VIVUS or designee is to be notified within 1 business day of awareness of the event. In particular, if the SAE is fatal or life-threatening, notification to VIVUS or designee must be made immediately, irrespective of the extent of available adverse event information. This timeframe also applies to additional new information (follow-up) on previously reported SAE.

In the event that the investigator does not become aware of the occurrence of an SAE immediately (e.g., if an outpatient study subject initially seeks treatment elsewhere), the investigator is to report the event within 1 business day after learning of it and document the time of his/her first awareness of the adverse event.

For all SAEs, the investigator is obligated to pursue and provide information to VIVUS or designee in accordance with the timeframes for reporting specified above. In addition, an investigator may be requested by VIVUS or designee to obtain specific additional follow-up information in an expedited fashion. This information may be more detailed than that captured on the adverse event CRF. In general, this will include a description of the SAE in sufficient detail to allow for a complete medical assessment of the case and independent determination of possible causality. Information on other possible causes of the event, such as concomitant medications and illnesses, must be provided. In the case of a subject death, a summary of available autopsy findings must be submitted as soon as possible to VIVUS or its designee.

11.4.2 Non-Serious Adverse Event Reporting Requirements

Non-serious adverse events are to be reported on the Adverse Event CRFs, which are to be submitted to VIVUS or its designee.

11.4.3 Pregnancy

If any study subject becomes or is found to be pregnant while receiving the investigational product, the investigator must immediately discontinue study treatment and report the pregnancy to VIVUS or designee within 1 business day of learning of the pregnancy.

The investigator will follow the pregnancy until completion or until pregnancy termination (i.e., elective pregnancy termination) and then notify VIVUS or designee of the outcome. The investigator will provide this information as a follow-up to the initial pregnancy report.

For reported pregnancies that result in a live birth, the status of the newborn should be assessed at the time of birth. The status of an aborted fetus should be assessed by gross visual inspection, unless pre-abortion test findings are suggestive of a congenital anomaly.

If pregnancy outcomes meet the criteria for classification as SAEs (i.e., stillbirth, neonatal death, or congenital anomaly), the investigator should follow the procedures for reporting SAEs.

Similarly, any pregnancy outcomes that are considered to be adverse events should be reported as such on the appropriate CRF. However, pregnancy in itself need not be reported as an adverse event if there is no associated adverse outcome.

For reporting purposes, ectopic pregnancies should be reported as SAEs, but because the fetus is not potentially viable, they need not be reported as a pregnancy.

12.0 STATISTICAL PLAN

12.1 Statistical Analysis

Detailed methodology for summary and statistical analyses of the data collected in this clinical trial will be documented in a Statistical Analysis Plan (SAP). This document may modify the plans outlined in the protocol; however, any major modifications of the primary endpoints definition and/or its analysis will also be reflected in a protocol amendment. Additional statistical analyses other than those described in this section may be performed if deemed appropriate and included in the plan. The SAP will be finalized and signed prior to the finalization of the database.

12.2 Sample Size Determination

In previous studies in adults, VI-0521 mid-dose (PHEN/TPM 7.5 mg/46 mg) resulted in a placebo-subtracted BMI reduction of 2.4 units with a standard error approximately 0.16 units and a within treatment standard deviation of 2.9. A very conservative estimate of the treatment difference between the mid-dose and placebo would be 2 units of BMI which represents more than 2 standard errors below what was observed before. If we enroll 200 subjects (50 placebo, 50 mid-dose, and 100 top-dose), we will have at least 90% power to detect a statistically significant difference between the top-dose (PHEN/TPM 15 mg/92 mg) and the placebo because we could assume that the top-dose will have a higher effect size than the mid-dose. This

calculation assumes that there will be an approximately 30% dropout rate. This sample size will also provide approximately 80% power to detect a statistically significant difference between the mid-dose and placebo.

12.3 Analysis Populations

Three different analysis populations will be used for analysis of data from this study, as described below:

- Randomized: This population will be comprised of all subjects who were initially randomized. This population will be used for summaries of subject disposition and baseline subject characteristics.
- Intent-to-treat (ITT)/Safety: This population will be comprised of all subjects who were initially randomized and received at least one dose of study drug. This will be the primary population for all summaries of subject disposition and baseline characteristics, efficacy analyses, and safety analyses for purposes of regulatory submissions.
- Modified Intent-to Treat (m-ITT): This population will be comprised of all randomized study subjects who receive study treatment and return for at least one post-randomization assessment of height and weight. This population will be used for the analysis of all efficacy variables for all other purposes, including but not limited to publications, presentations, and robustness of sensitivity of analyses.

12.4 Subgroups

BMI change will be tabulated by age and gender. Additionally, further exploratory subgroup analyses of the primary efficacy endpoints may include evaluation by race and/or other subgroups deemed medically and/or scientifically important.

12.5 Statistical Methods

12.5.1 Analysis of the Primary Endpoint

The primary endpoint for this study is the mean % change in BMI from baseline to end of study (Week 56).

Comparisons in the primary endpoint of change from the baseline BMI between treatment groups be assessed for the ITT population using a mixed effects model with repeated measures (MMRM) with factors of treatment, visit, treatment by visit interaction, baseline BMI value, age stratification, and gender stratification. Appropriate contrast will be applied for treatment comparisons at Week 56. The pairwise comparisons of interest are top-dose vs. placebo, and mid-dose vs. placebo, and top-dose vs. mid-dose. The primary null hypothesis will be that there is no treatment difference between any VI-0521 treatment groups and the placebo in the percent change from baseline to Week 56 in BMI. An appropriate contrast will be used for the comparisons at Week 56. The family-wise type 1 error for the comparisons will be controlled by Fisher's protected least significant difference (LSD) method at the 0.05 significance level: placebo, mid-dose, and top-dose will be first compared for overall difference in the percent change from baseline in BMI. Once the overall difference is significant at the 0.05 significance level, the above 3 pairwise comparisons will be conducted using Fisher's LSD method at the

0.05 significance levels. The order for comparisons of interest is top-dose vs. placebo, mid-dose vs. placebo, and top-dose vs. mid-dose. Due to the fact that only three treatments are compared, the above procedure strongly controls the family-wise type 1 error.¹¹

12.5.2 Method for Prevention and Treatment of Missing Values

For subjects who discontinue treatment prior to trial completion, every attempt will be made to have them continue with clinic visits and study assessments. Particular attention will be given to collecting Week 56 assessments of weight and height, regardless of when subjects discontinued treatment.

The above MMRM method used for the analysis of the primary endpoint has an inherent mechanism for imputing missing data. Therefore, MMRM is applied to the m-ITT population with the observed data without imputation. The following sensitivity analyses may be considered to explore the impact of missing data on the conclusion of the primary analysis. The details of the sensitivity analyses will be included in the statistical analysis plan.

The first sensitivity analysis is using a multiple imputation method based on the monotonic missing pattern under the assumption of missing at random (MAR). The intermittent missing data will be imputed using multiple imputation MCMC (Markov chain Monte Carlo) procedure.

The second sensitivity analysis is also using multiple imputation, however, under the assumption of missing not at random (MNAR) to explore the validity of MAR using pattern-mixture model:

- 1) For subjects who discontinue study participation prior to Week 56 and do not have follow-up visit, the missing data will be imputed using the observed data from the subjects in the same arm who discontinue the study treatment but have the primary endpoint measurement in the follow up visit using a regression method. The intermittent missing data will be imputed using multiple imputation MCMC procedure. an ANCOVA model using a similar mixed procedure (without the repeated measures) as the primary analysis will be applied to these multiple-imputed % change in BMI at Week 56 with treatment, baseline BMI value as a covariate, and age and gender as stratification factors. The results of ANCOVA analysis on the multiple imputed datasets will be combined and summarized.
- 2) Tipping point analyses: Subjects from the treatment arm who drop out the study will have their unobserved efficacy data imputed by the observed data from completers in the same arm using the multiple imputation method based on the monotonic missing pattern under the assumption of missing at random (MAR) with the resulting imputed values further worsened by an amount δ . Subjects who drop out the study from the control arm will be assumed to exhibit the same evolution of the disease as the completers in control arms and their values will be imputed by the multiple imputation method based on the monotonic missing pattern under the assumption of missing at random (MAR) above without the addition of δ . Sensitivity analysis may be performed for a range of δ to find a “tipping point” value of δ at which study conclusions start to change. When $\delta=0$ the missing data are assumed to be MAR. When $\delta > 0$, the missing data are assumed to be MNAR.

The third sensitivity analysis is the last observation carried forward (LOCF). For those subjects who discontinue study participation prior to Week 56, the last observed weight and height will be

used to derive the change in BMI.

Similar analyses will be performed for the primary endpoint for the m-ITT population.

12.5.3 Analysis of the Secondary Endpoints

If both the mid- and top-doses are shown to be statistically significantly better than placebo for the primary endpoint using the Fisher's LSD procedure, then the secondary endpoints will be tested in a stepwise way to preserve the familywise type 1 errors. Details of the stepwise testing procedure for secondary efficacy endpoints will be described in a prospective SAP.

Percent of subjects achieving a reduction $\geq 5\%$ from baseline in BMI at Week 56 will be analyzed using a logistic regression, with treatment, age and gender stratification as the main effect and baseline BMI value as a covariate at the 0.05 significance level. The adjusted odds ratios between the top-dose and placebo and between the mid-dose and placebo will be calculated together with their 95% confidence intervals. The p-values for the comparisons will also be generated.

The percent of subjects achieving a reduction $\geq 10\%$ and $\geq 15\%$ from baseline in BMI at Week 56 will be analyzed similarly.

Secondary efficacy endpoints that are continuous variables will be analyzed by a similar MMRM model as for the primary endpoint where the baseline BMI value will be replaced by the baseline value of the corresponding endpoint as a covariate.

The above analyses will be conducted for both the ITT and m-ITT populations.

12.6 Safety Analysis

All safety analyses will be done for the ITT population. Safety data will be summarized for all treatment groups.

Safety will be assessed by an evaluation of adverse events (each study visit); laboratory parameters (screening, periodically during the study and end of study); electrocardiograms; physical examinations (screening, end of study); PHQ-9: Modified for Teens (see [Appendix 4](#)), C-SSRS, and vital signs, at each study visit). Descriptive statistics will be generated for the questionnaire data.

12.6.1 Analysis of CANTAB

CANTAB will be scored according to its instructions. The scores will be summarized by treatment descriptively.

12.6.2 Analysis of Hand and Wrist X-Ray

Changes from baseline to Week 56 in hand and wrist X-ray will be evaluated. Differences between treatment groups will be evaluated using methods similar to those used to evaluate other continuous variables.

12.6.3 Analysis of DXA

In the subset of subjects treated at sites where DXA scans are being done, mean changes from

baseline to Week 56 in bone mineral density (BMD) and bone mineral content (BMC)-Z scores will be evaluated. The mean change in BMD and BMC will be summarized descriptively as a continuous variable.

12.6.4 Adverse Events

Adverse events will be coded using a MedDRA coding dictionary. The number and percentage of subjects who reported at least one adverse event in each system organ class and preferred term category, and the total number and percentage of subjects with any AE over all system organ classes will be summarized by treatment group.

Subsets of AEs that are considered serious or required discontinuation of the study medication will be summarized separately and listed by subject.

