6.0 STUDY DESIGN

In this multicenter, randomized, double-blind, placebo-controlled, parallel-design study, approximately 200 subjects will be enrolled at approximately 20 sites in the United States. Subjects will be randomly assigned in a 1:1:2 ratio to placebo, $N= 50$; mid-dose (PHEN/TPM 7.5 mg/46 mg), $N= 50$; or top-dose (PHEN/TPM 15 mg/92 mg), $N=100$, of VI-0521, to be taken orally once daily in the morning. Randomization will be stratified by age (12-14 vs 15-16 years old) and gender. The study will consist of a screening period of up to 28 days, followed by a 56-week treatment period.

[figure not shown]
Subjects will be instructed to follow a mild hypocaloric diet modification program representing a 500-calorie/day deficit and to implement a family-based lifestyle modification program for adolescents, as tolerated, throughout the study period. The lifestyle program will include physical activity, behavior change, and family support. The same lifestyle modification program, specific to this population, will be implemented across all sites. Study drug will be titrated as described in Section 8.4.1.

Subjects who are unable to tolerate the assigned dose may be treated at a reduced dose level or may take a drug holiday as defined in Section 8.4.4. In addition, for growth monitoring, investigators will monitor rates of weight loss in treated subjects. For subjects with baseline BMI 95-98th percentile, reduce study drug dosage when BMI is < 85th percentile or when weight loss exceeds an average of 2 lbs (0.9 kg) per week. For subjects with baseline BMI $\geq 99^{th}$ percentile, reduce study drug when weight loss exceeds an average of 2 lbs (0.9 kg)/week.

All subjects will return at approximately 4-week intervals for study assessments. All female

subjects will undergo a pregnancy test at each visit. Subjects who discontinue study drug during the study will be encouraged to remain on study (off study drug) for continued follow-up by attending all remaining visits and have all study-related procedures performed, and to return at the 56-week time point for measurements and evaluations. For those who choose to completely withdraw from the study at any point, the end of study (Week 56) procedures should be completed.

Figure 1. Schematic Diagram of Study Design

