### **4.2 Safety**

This population will be comprised of all subjects who were initially randomized and received at least one dose of study drug. This will be the primary population for all summaries of subject disposition and baseline characteristics, and safety analyses for purposes of regulatory submissions. The safety population is based on the treatments actually received.

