## 6. Statistical Methods

### 6.1 General Principles

All data processing, summarization and analyses will be performed using SAS Environment / Version 9.3 (or later) of the SAS® statistical software package.

The following principles will be applied to all TFLs unless otherwise stated:

Principle	Value
Significant tests	Two-sided and use a 5% significance level.
Treatment group labels and order presented	Placebo VI-0521 Mid VI-0521 Top
Tables	Data in summary tables presented by treatment group, assessment and visit (where applicable).
Listings	All data collected presented by treatment group, site, subject, and visit (where applicable), unless otherwise specified.
Descriptive summary statistics for continuous variables	Number of observations (N), mean, standard deviation (SD), minimum, median and maximum.
Descriptive summary statistics for categorical variables	Frequency counts and percentages [n (%)].
Denominator for percentages	Number of subjects in the pertinent analysis population, unless stated otherwise in table shells.
Include "Missing" as category	Demographics and Other Baseline Characteristics only
Display for 0 percentages	Blank
Display to one more decimal place than collected value	Mean Median Minimum Maximum
Display to two more decimal places than collected value	Standard Deviation Confidence Interval
Limit of precision for displays	3 decimal places
Date Format	DDMMYYYY

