### 6.7.6 Adverse Events

All adverse events (AEs) recorded on the eCRF will be coded using the MedDRA dictionary Version 21.1 (or a later version if updated during the study) and classified as either pre-treat AEs or treatment – emergent AEs (TEAEs) as follows:

- Pre-treat AEs are events that start prior to the date of first dose of study treatment.
- TEAEs are events with start date on or after the date and time of first dose of study treatment and up to 28 days after date and time of last dose of study treatment or events with start date and time prior to the date and time of first dose of study treatment whose severity worsens on or after the date and time of first dose of study treatment.

All AE data will be listed by treatment group. Treatment-emergence status will be flagged in the listing. In addition, corresponding listings of serious AEs (SAEs), AEs leading to discontinuation of study treatment and AEs resulting in death will be produced.

Summary tables of TEAEs by treatment group will be produced for the Safety population.

The severity of all AEs is recorded as mild, moderate, or severe. If severity is missing for a TEAE, it will be considered severe only in the overall category in the summary tables.

The relationship between an AE and study treatment is assessed as Related or Not Related by the investigator.

An overview table will summarize the number and percentage of subjects with at least one of the following TEAEs, where subjects with more than one TEAE in a particular category are counted only once in that category:

- Any TEAE
- Any TEAE by severity (mild, moderate, severe)
- Drug-related TEAE
- TEAE leading to dose reduction
- Drug-related TEAE leading to dose reduction
- TEAE leading to study treatment discontinuation
- Treatment-emergent SAE
- Drug-related Treatment-emergent SAE
- Treatment-emergent SAE leading to death;
- Drug-related Treatment-emergent SAE leading to death
- Treatment-emergent SAE leading to treatment discontinuation

The number and percentage of subjects reporting each TEAE will be summarized by System Organ Class (SOC) and Preferred Term (PT) for the Safety population. Tables will be sorted alphabetically by SOC. PTs will be sorted by descending overall total. The following summaries will be produced:

- TEAEs by SOC and PT
- Drug-related TEAEs by SOC and PT
- TEAEs by maximum severity by SOC and PT
- TEAEs related to treatment by maximum severity by SOC and PT

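### Adverse events are tabulated only as crude percentages with no summary of exposure, so unequal stopping between arms would distort comparisons of events that build up over the year

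*Protocol*

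**What the plan says.** Protocol section 12.6.4 reports "The number and percentage of subjects who reported at least one adverse event in each system organ class and preferred term category", by treatment group. SAP section 6.7.6 follows it: "The number and percentage of subjects reporting each TEAE will be summarized by System Organ Class (SOC) and Preferred Term (PT) for the Safety population". In the SAP's overview table, "subjects with more than one TEAE in a particular category are counted only once in that category".

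The default denominator in SAP section 6.1 is "Number of subjects in the pertinent analysis population, unless stated otherwise in table shells". For adverse events that is the Safety population of SAP section 4.2: "all subjects who were initially randomized and received at least one dose of study drug".

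Two different end points apply to follow-up for adverse events:

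- **Counting in the tables (SAP 6.7.6):** an event is treatment-emergent if it starts "up to 28 days after date and time of last dose of study treatment".
- **Collection (Protocol 11.3):** reporting "extends until 28 calendar days after the last day of study participation".

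Protocol 6.0 plans a screening period "followed by a 56-week treatment period" and encourages subjects who stop drug to keep attending visits. For those subjects, collection runs on after counting in the tables has ended. SAP 6.7.6 lists all adverse events with treatment emergence flagged, so later events appear in the listing but not in the tables.

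**The concern.** A subject who stops drug at Week 8 is at risk in the tables for 8 + 4 = 12 weeks. A completer is at risk for 56 + 4 = 60. Each counts as one full subject in the denominator. If stopping differs between arms, the arm with more of it has less time in which to record events, and its percentages fall for that reason alone.

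The nearest planned summaries do not supply what is missing. Capsule compliance (SAP 6.5) divides by the days of study treatment, so a subject who stops early can still score 100%. Disposition (SAP 6.2) counts subjects who stop and their reasons, but not when they stopped.

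Time at each dose level matters as well. In Table 1 of Protocol 8.4.1, the top-dose arm first receives its assigned dose in Weeks 15-16, and Protocol 8.4.4 allows blinded dose reduction. A top-dose subject who stops at Week 8 counts fully in that arm without having received that dose. Safety is one of the primary objectives (Protocol 5.0), so both the active-placebo and the mid-top contrasts need to be readable.

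**Working it through.** **Text check.** Protocol 12.6 and SAP sections 6.2, 6.5 and 6.7 contain no extent-of-exposure table, no rate per unit of time at risk, no time-to-event summary of adverse events and no summary of time at each dose level. The plan states no figure on this point, so there is none to reproduce.

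**Inputs from the documents.** Treatment lasts 56 weeks (Protocol 6.0). The counting tail is 28 days, or 4 weeks (SAP 6.7.6). The full window is therefore 60 weeks. Dropout of about 30% is expected overall and is not given by arm (Protocol 12.2).

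**Assumptions, not in the documents.** The event rate is constant and identical in two arms. Risk over the full window is R = 20%. A proportion s of subjects stop early, 15% in one arm and 45% in the other (unweighted mean 30%). Stopping is independent of events, with times uniform over 0 to b weeks, where b = 56 (spread) or b = 20 (early).

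**Formulas.**

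- λ = −ln(1 − R)/60 = −ln(0.8)/60 = 0.003719 per week.
- Risk by time u: F(u) = 1 − exp(−λu).
- Mean risk in early stoppers: F̄(b) = 1 − [exp(−4λ) − exp(−(b + 4)λ)]/(bλ).
- Crude percentage = (1 − s) × R + s × F̄(b).

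**Spread stops.** F̄(56) = 0.1106.

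- s = 15%: 0.85 × 0.20 + 0.15 × 0.1106 = 18.7%.
- s = 45%: 0.55 × 0.20 + 0.45 × 0.1106 = 16.0%.

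**Early stops.** F̄(20) = 0.0505.

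- s = 15%: 0.85 × 0.20 + 0.15 × 0.0505 = 17.8%.
- s = 45%: 0.55 × 0.20 + 0.45 × 0.0505 = 13.3%.

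The true rates are equal, yet the crude ratios are about 0.86 and 0.75. At R = 50% the same steps give 47.0% versus 40.9% (spread) and 44.7% versus 34.1% (early). Which arm stops more decides the direction of the error. With the same s and b in both arms the two percentages are equal.

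**Events confined to the first weeks.** Put all the risk in the first 8 or 16 weeks and keep the 15% versus 45% split. For R = 20% or 50%, the crude ratios are 0.93 to 1.00, so crude percentages hardly suffer. First events per subject-year then give ratios of 1.13 to 1.32, a spurious excess in the arm with more stopping. A simple rate is therefore not a safe replacement.

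**The case against.** The strongest reply is that the number and percentage of subjects is a valid descriptive summary and that the plan already shows much of what a reader needs. By arm, SAP 6.2 gives the numbers who complete on drug, who stop drug and leave, and who stop drug but stay, with reasons for discontinuation. SAP 6.7.6 adds events leading to dose reduction and to discontinuation. Unequal stopping would therefore be visible. This stands. What remains hidden is its timing and its effect on time at risk.

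A subject who stops because of an adverse event is already counted for that event. The calculation above treats stopping as independent of events, so it does not describe intolerance-driven stopping for the any-event and leading-to-discontinuation categories. This stands too. Other event types in the same subjects can still be missed.

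The split is an assumption. With 1:1:2 allocation, 15% on placebo and 45% in both active arms would be (50 × 0.15 + 150 × 0.45)/200 = 37.5% overall, more than the planned 30%. The artefact at 20% risk is 2.7 to 4.5 percentage points. The 95% half-width for a difference is about 15.7 points for 50 versus 50, from 1.96 × √[0.2 × 0.8 × (1/50 + 1/50)], and 13.6 for 50 versus 100. SAP 6.7.6 also plans no statistical comparison of adverse events. These points limit the harm.

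A reader might infer that the protocol itself truncates adverse events, or that late off-drug events are lost. Neither is so: the cut-off is in the SAP's definition, and the listing keeps those events. A reader might also infer that a drug effect will be hidden or created. The documents do not support that, because they give no discontinuation by arm. Finally, the table shells were not available and SAP 6.1 lets them change denominators, so the statement about denominators rests on the default rule.

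**Conclusion.** The gap is real and modest. As written, the plan reports crude percentages over follow-up that varies with time on drug, and tabulates no exposure by arm or dose level. The distortion requires unequal stopping between arms and events that accrue over the year. Under the assumed 15% versus 45% split, constant equal rates and a 20% full-window risk, it is 2.7 points (spread stops) to 4.5 points (early stops). With equal stopping patterns and equal event rates it is nil, and for events confined to the first weeks it is small. The crude tables should stay. What is missing is a companion summary that lets a reader judge them, and specifying it in advance avoids choosing a safety measure after unequal stopping has been seen. This is a cheap improvement, not a flaw that invalidates the safety analysis.

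**What to change.** Keep the crude percentages and add to SAP 6.7.6:

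1. An extent-of-exposure table by arm: weeks on drug, total subject-years and weeks at each dose level.
2. Descriptive time-to-first-event cumulative incidence by arm for any treatment-emergent event, serious events, events leading to discontinuation and common preferred terms. State how follow-up ends: last dose plus 28 days in one version, and the full Protocol 11.3 collection period, with all collected events, in a second. The first version treats stopping as uninformative about later events, and the second relies on that less.

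Rates per 100 subject-years may be added as a supplement. A note should say that they assume a constant rate and can overstate early-onset events in the arm with more stopping.

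Any intervals should be labelled descriptive. The sentence in SAP 6.7.6 that rules out statistical comparisons should be reworded to allow intervals without tests.

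The cost is SAP wording, programming from dates already recorded (Protocol 7.3 and 8.4.4 require the last-dose date) and a few more tables. No new data, visits or changes to blinding are needed.
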